13.5 Secondary Objectives, Endpoints, Analysis Plans

The secondary objectives include to determine the persistence and stability of serologic GMT of HPV types 6/11/31/33/45/52/58 between 6, 12, 18, and 24 months after prime dose and prior to the administration of the second dose and to assess safety and reactogenicity to each vaccine dose. The secondary endpoints are the antibody levels at 6, 12, 18, and 24 months for each HPV type. Similarly to the primary endpoint analysis, for evaluating persistence and stability of serologic GMT of each HPV type we propose to perform a one-sided paired t test to evaluate the difference in the mean of log-transformed antibody level between 6 and 12 months, between 12 and 18 months and between 18 and 24 months, respectively, to evaluate whether the GMT at 12/18/24 months is not inferior to the GMT at 6/12/18 months. In addition, percentage of participants whose type-specific antibody levels decrease, increase, or remain stable between the 6 and 12 month study visits, between the 12 and 18 month study visits and between the 18 and 24 month study visits will be reported along with the associated 95% confidence interval. A linear mixed effects model with BMI, time and the interaction between BMI and time as the covariates will be performed on antibody level data measured at 6, 12, 18, and 24 months to evaluate whether BMI affects the changes in each specific antibody level.

Similar to the primary analyses, we will perform all of the secondary and exploratory analyses separately for girls and boys. In addition, for all of the secondary and exploratory analyses, adjustment for multiple comparisons will not be performed. However, the number of comparisons will be reported and we will also cautiously interpret the findings. For both primary and secondary endpoints, if the normality assumption is violated, potential transformation will be sought or nonparametric methods such as signed rank test will be performed.

We will try to reduce the fraction of participants with missing outcomes as much as possible. The covariates (e.g. BMI, BSA, and sociodemographics) that are predictive of missing-ness for each outcome at each visit (i.e. 6, 12, 18 and 24 months) will be identified through use of logistic regression for each missing indicator and then incorporated into multiple imputation procedures to handle missing data while performing the statistical analysis for both primary and secondary endpoints.

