13. STATISTICAL CONSIDERATIONS

13.1 Study Design/Description

This is a single-arm, open-label, non-randomized, phase IIA trial to determine the immunogenicity of a prime and deferred-booster dosing schedule of a nonavalent prophylactic HPV vaccine (GARDASIL 9) among 9-11 year-old girls and boys. The primary endpoint analysis will be evaluating persistence and stability of serologic geometric mean titers (GMT) of HPV16/18 between 6, 12, 18, and 24 months after the prime dose/prior to administration of the second dose. If the HPV 16/18 antibody level at 12/18/24 months is not inferior to the HPV 16/18/24 antibody level at 6/12/18 months at a non-inferiority margin of 0.35 standard deviation, then the serologic GMT is considered as persistent and stable.

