13.4 Primary Objective, Endpoint(s), Analysis Plan

The primary objective of this study is to determine the persistence and stability of serologic geometric mean titer (GMT) of HPV 16/18 between 6, 12, 18, and 24 months after the prime dose and prior to the

administration of the second dose. The primary endpoints are the HPV 16/18 antibody levels at 6, 12, 18, and 24 months. To address the primary objective, the primary endpoint analysis will be evaluating persistence and stability of serologic geometric mean titers (GMT) of HPV16/18 between 6, 12, 18, and 24 months after the prime dose/prior to administration of the second dose. We first propose to perform a one-sided paired t test to compare the difference in the mean of the log-transformed antibody levels between 6 and 12 months, between 12 and 18 months, and between 18 and 24 months respectively, to evaluate whether the GMT at 12/18/24 months, respectively, is not inferior to the GMT at 6/12/18 months. Comparing the difference in the mean of the log-transformed antibody levels is equivalent to comparing the logarithm of the ratio of GMTs since GMT is equal to the exponentiation of log-transformed mean. Bonferroni correction will be used to correct for multiple comparisons (6 vs. 12, 12 vs. 18 and 18 vs. 24).

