The protocol was originally designed to assess the serologic response in girls. Amendment 4 includes the addition of a cohort of boys. Due to limits in the study completion timeline and available study budget, a smaller number of boys than girls will be included in the study to generate pilot data on the serologic response in boys. Boys have been shown to mount a higher serologic response than girls. Therefore, we expect boys and girls to have different responses to the vaccine and will perform the primary analyses for girls and boys separately. For girls, with a sample size of 100 and an overall significance level of 5% (based on Bonferroni correction, i.e. a 1.67% significance level for each test), there will be at least 90% power to detect a non-inferiority margin no greater than 0.35 standard deviations [23]. For boys, with a sample size of 39 and an overall significance level of 5%, there will be at least 80% power to detect a non-inferiority margin no greater than 0.50 standard deviations. In addition, similar to the analysis performed by Safaeian et al. [13], we will also evaluate the stability by categorizing the changes in antibody level from 6 months to 12 months. Specifically, a participant's antibody level at 12 months either remains within two-fold of the level at 6 months (considered as stable) or decreases/increases more than two-fold of the level at 6 months (same for the changes from 12 months to 18 months and from 18 months to 24 months). Percentage of participants whose type-specific antibody levels decrease, increase, or remain stable between the 6 and 12 month study visits, between the 12 and 18 month study visits and between the 18 month and 24 month study visits will be reported along with the associated 95% confidence interval. For girls, a sample size of 100 will produce a two-sided 95% confidence interval with a width ≤ 0.203 based on the exact method approach. For boys, a sample size of 39 will produce a two-sided 95% confidence interval with a width ≤ 0.328 based on the exact method approach.

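### The normality fallback lets the primary non-inferiority test be replaced after the titres are seen by one that tests the GMT ratio only if the changes are symmetric

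*Combined protocol and SAP*

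**What the plan says.** Section 13.1 states the decision rule for the GMT: if antibody at the later visit is not inferior to that at the earlier one "at a non-inferiority margin of 0.35 standard deviation, then the serologic GMT is considered as persistent and stable". Section 13.4 names the test: "We first propose to perform a one-sided paired t test to compare the difference in the mean of the log-transformed antibody levels", applied to 6 v 12, 12 v 18 and 18 v 24 months. It explains why this answers a question about the GMT: the comparison is "equivalent to comparing the logarithm of the ratio of GMTs since GMT is equal to the exponentiation of log-transformed mean". The level is set "based on Bonferroni correction, i.e. a 1.67% significance level for each test". The power statement uses 100 girls with a margin of 0.35 SD and 39 boys with 0.50 SD.

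The fallback comes in section 13.5, which deals with secondary objectives, but its sentence covers primary and secondary endpoints alike: "if the normality assumption is violated, potential transformation will be sought or nonparametric methods such as signed rank test will be performed". The plan does not name a normality test or cut-off, the transformation, how to choose between the two routes, or a margin on any new scale. The same section wants covariates that predict missingness to be "incorporated into multiple imputation procedures to handle missing data while performing the statistical analysis for both primary and secondary endpoints".

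**The concern.** Normality of the paired changes can be judged only once the titres are in hand, so the choice of primary test depends on the data. The two routes differ.

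- **Further transformation.** The titres are already logged. The equivalence in section 13.4 holds for the mean of the logs and for no other scale, so the margin would have to be defined again.
- **Signed rank test.** Applied to log differences shifted by the margin, it stays on the log scale, but it tests the centre of a symmetric distribution (the pseudomedian). This equals the mean log change only under symmetry.

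If most children hold their titre and a minority wane sharply, the changes are left-skewed. The mean then lies below the pseudomedian, and the signed rank test can pass when the GMT has fallen by the whole margin. With right skew it can fail when the GMT has not fallen at all. What is at stake is the claim that the GMT is persistent and stable, and the power promised for it.

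A smaller gap, not quantified here: the plan does not say how a signed rank result would be combined across imputed data sets.

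**Working it through.** **Inputs from section 13.4.** One-sided α = 0.05/3 = 0.0167 per test; girls n = 100, margin m = 0.35 SD; boys n = 39, m = 0.50 SD.

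**Assumptions.** The SD is that of the paired log differences. The switch is Shapiro-Wilk p < 0.05. The shapes of the changes are illustrative.

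**1. The plan's own power.** With no true change, power = P(T > t(1-α, n-1)), where T is noncentral t with n-1 degrees of freedom and noncentrality m√n.

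- Girls: 0.35 × √100 = 3.50, power 90.9% (plan: at least 90%).
- Boys: 0.50 × √39 = 3.12, power 81.6% (plan: at least 80%).

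Both reproduce, so the planned power is that of the paired t test.

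**2. What each test targets.** Let D be the later minus the earlier log titre, with SD σ. Then E(D) is the log GMT ratio, and the t test addresses E(D) ≤ -mσ. The signed rank test on D + mσ asks whether the pseudomedian exceeds zero. At E(D) = -mσ the pseudomedian is zero under symmetry, above zero under left skew and below zero under right skew.

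**3. False non-inferiority at the margin.** E(D) is set to exactly -mσ (nominal 1.67%). Skewed changes are standardised gamma variables of shape k, reflected for left skew; skewness is 2/√k, so k = 16, 4, 1 gives 0.5, 1, 2.

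| Changes | Girls, t | Girls, with switch | Boys, t | Boys, with switch |
|---|---|---|---|---|
| Normal | 1.7% | 1.9% | 1.7% | 1.8% |
| Laplace (symmetric, heavy tails) | 1.7% | 1.8% | 1.6% | 1.7% |
| Skewness -0.5 | 2.2% | 4% | 2.1% | 2.7% |
| Skewness -1 | 2.7% | 10% | 2.8% | 5.1% |
| Skewness -2 | 3.9% | 32% | 4.8% | 14.4% |

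A run of 40,000 trials put the t test at 2.1 / 2.3 / 3.4% (girls) and 2.2 / 2.9 / 4.6% (boys) for the three skewed rows. With 4,000 trials the simulation standard error is √(0.32 × 0.68/4000) = 0.7 points at 32% and √(0.02 × 0.98/4000) = 0.2 points at 2%.

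At skewness -2 with a GMT fall of 1.25 times the margin, the signed rank test still passes 9.8% of girls' trials, against 0.4% for the t test.

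**4. A waning subgroup, girls.** Changes are N(0, 0.3) in natural-log units, with a fraction p falling by an extra d. Setting pd = m√(0.09 + p(1-p)d²) gives d = 0.3m/√(p² - m²p(1-p)). For p = 0.15: d = 0.105/√(0.0225 - 0.1225 × 0.1275) = 0.105/0.0830 = 1.27, a fall of e^1.27, about 3.5-fold, and a GMT ratio of e^(-0.15 × 1.27) = 0.83.

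| Fraction waning | Fall | False pass with switch |
|---|---|---|
| 15% | 3.5-fold | 30.6% |
| 20% | 2.1-fold | 5.7% |
| 25% | 1.7-fold | 2.3% |
| 30% | 1.5-fold | 1.6% |

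The normality check fires in 100% of runs at 15%, about 59% at 20% and about 16% at 25%. At 12% the required fall is 15-fold and the signed rank test passes about 97% of trials. For boys the rate with the switch is 3.1% at p = 30% and 1.7% at 35%.

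**5. Power with no true change, girls.** Right skew +1 / +2: about 93% / 95% with t, 74% / 52% with signed rank, against the stated 90%.

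The further-transformation route was not simulated, because the plan names no transformation.

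**The case against.** The strongest reply has four parts.

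- **Nothing in the documents says the changes are left-skewed.** Symmetric heavy tails also set off the switch (79% of girls' runs under Laplace changes). There the signed rank test still targets the mean log change, holds its level and gains power. This stands: non-normality alone does no harm, and a reader who infers that the fallback fires only where it misleads goes too far.
- **The subgroup result is steep.** It moves from about 31% to nominal as the waning fraction goes from 15% to 30%. This also stands, so no single figure can be given as the expected error.
- **A waning subgroup would be seen.** Section 13.4 requires the percentage of participants whose level falls or rises more than two-fold in each interval, with exact 95% confidence intervals. It would show 15% of girls falling 3.5-fold. It does not correct the formal test on which the persistence claim rests.
- **The t test is not exact either.** At skewness -2 it runs at 3.9% (girls) and 4.8% (boys), two to three times nominal. True, but in the same cases the switch gives 32% and 14.4%.

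This is also a single-arm Phase IIA trial whose boys' cohort is meant for pilot data. That limits the consequences, but the girls' analysis is a formal test with a stated level and power.

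**Conclusion.** The concern holds in a limited form. As written, section 13.5 allows a data-dependent replacement of the primary test by one that addresses the GMT ratio only if the changes are symmetric, or by a transformation on whose scale the margin is undefined. With the GMT fall at the margin, girls' false-pass rate ranges from about 2% (symmetric changes) to about 32% (skewness -2), and in the tabulated subgroup cases from 1.6% to about 31%. For boys it is 2.7%, 5.1% and 14.4% at skewness -0.5, -1 and -2. Under right skew the loss is in power.

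The direction follows from what the two tests measure. The size rests on assumed shapes, an assumed normality check, and the SD being that of paired differences.

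A reader might infer that about one trial in three would pass falsely. The documents do not support that: they give no distribution of changes, and milder shapes bring the rate close to nominal. Nor should a reader infer that keeping the t test gives exact control under strong left skew. It is nearer nominal, and it tests the quantity the plan says it wants.

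**What to change.** Before the titres are analysed, amend the fallback sentence in section 13.5 and state the rule in section 13.4:

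- For the non-inferiority tests, delete the data-driven switch. The only primary analysis is the mean paired difference in log titre, reported as a GMT ratio with its one-sided t-based confidence limit, whatever a normality check shows.
- Name a bootstrap-t limit for the same GMT ratio as a sensitivity analysis. It addresses the t test's own inflation under left skew. The evidence is thin: a 1.7% false-pass rate in the 15% subgroup case only, from 600 trials of 1,000 resamples.
- Report signed rank results as supportive only, and keep the two-fold change table beside the primary result.

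The cost is SAP wording and one bootstrap run, with no new data and no change in sample size. The downside is that with symmetric, heavy-tailed changes the t test gives up power to the signed rank test: about 89% against 96% for girls and 81% against 89% for boys under Laplace changes. It still stays near the planned 90% and 80%.

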13.6 Reporting and Exclusions

If a participant has received all doses of the vaccine, he/she will be considered compliant (as defined in 5.7) for statistical analysis. Participants who are considered off-agent (see section 8.3) will continue to be followed, if possible, for safety reasons and in order to collect endpoint data according to the schedule of events. As mentioned earlier in the primary and secondary analyses, if a subject has missing data on some primary or secondary endpoints, multiple imputation techniques will be used to handle missing data.

13.7 Evaluation of Toxicity

All participants will be evaluable for toxicity from the time of their first dose of vaccine. Descriptive statistics of the type and frequency of all adverse events will be generated, including 95% confidence intervals.

13.8 Evaluation of Response

All subjects with endpoint data will be assessed for response, based on the endpoints described above in Sections 13.4 and 13.5.

Sub-analyses may be performed on the subsets of participants, excluding those for whom major protocol deviations have been identified (e.g., early discontinuation of study, major protocol violations, etc.). However, sub-analyses may not serve as the basis for drawing conclusions concerning efficacy, and the reasons for excluding participants from the analysis should be clearly reported.

13.9 Interim Analysis

No formal interim statistical analyses are planned for this Phase IIA trial. Accrual, data collection, and any adverse events will be monitored on a regular basis.

13.10 Ancillary Studies

None.

14. ETHICAL AND REGULATORY CONSIDERATIONS

14.1 Form FDA 1572

Prior to initiating this study, the Protocol Lead Investigator at the Lead or Participating Organization(s) will provide a signed Form FDA 1572 stating that the study will be conducted in compliance with regulations for clinical investigations and listing the investigators, at each site that will participate in the protocol. All personnel directly involved in the performance of procedures required by the protocol and the collection of data should be listed on Form FDA 1572.

14.2 Other Required Documents

14.2.1 Signed and dated current (within two years) CV or biosketch for all study personnel listed on the Form FDA 1572 and Delegation of Tasks form for the Lead Organization and all Participating Organizations.

14.2.2 Current medical licenses (where applicable) for all study personnel listed on Form FDA 1572 and Delegation of Tasks form for the Lead Organization and all Participating Organizations.

14.2.3 Lab certification (*e.g.*, CLIA, CAP) and lab normal ranges for all labs listed on Form FDA 1572 for the Lead Organization and all Participating Organizations.

14.2.4 Documentation of training in “Protection of Human Research Subjects” for all study personnel listed on the FDA Form 1572 and Delegation of Tasks form for the Lead Organization and all Participating Organizations.

14.2.5 Documentation of Federalwide Assurance (FWA) number for the Lead Organization and all Participating Organizations.

14.2.6 Signed Investigator’s Brochure/Package Insert acknowledgement form

14.2.7 Delegation of Tasks form for the Lead Organization and all Participating Organizations signed by the Principal Investigator for each site and initialed by all study personnel listed on the form

14.2.8 Signed and dated NCI, DCP Financial Disclosure Form for all study personnel listed on Form FDA 1572 for the Lead Organization and all Participating Organizations

14.3 Institutional Review Board Approval

Prior to initiating the study and receiving agent, the Investigators at the Lead Organization and the Participating Organization(s) must obtain written approval to conduct the study from the NCI DCP CPC CIRB (referred to as CIRB) . Should changes to the study become necessary, protocol amendments will be submitted to the DCP PIO according to DCP Amendment Guidelines. The DCP-approved amended protocol must be approved by the CIRB prior to implementation.

14.4 Informed Consent

All potential study participants' legal representatives will be given a copy of the CIRB-approved Informed Consent to review. The participant will be given a copy of the CIRB-approved assent form. The investigator will explain all aspects of the study in lay language and answer all questions regarding the study. If the participant's legal representative agrees to allow him/her to participate in the study, the representative will be asked to sign and date the Informed Consent document. The participant will be asked to sign the assent form. The study agent(s) will not be released to a participant whose legal representative has not signed the Informed Consent document. Subjects who refuse to participate or who withdraw from the study will be treated without prejudice.

Prior to study initiation, the informed consent document and assent document will be reviewed and approved by the Consortium Lead Organization (CLO), NCI, DCP, and the CIRB. Each CLO and Participating organization at which the protocol will be implemented will also submit the study for Local IRB notification per site SOPs. Any subsequent changes to the informed consent/assent will be submitted by the Consortium Lead Organization to NCI DCP for approval and then to the CIRB, and then submitted to each organization's IRB for notification prior to initiation.

14.5 Submission of Regulatory Documents

All regulatory documents are collected by the Consortia Lead Organization and reviewed for completeness and accuracy. Once the Consortia Lead Organization has received complete and accurate documents from a participating organization, the Consortium Lead Organization will forward the regulatory documents to the DCP Regulatory Contractor:

Paper Document/CD-ROM Submissions:

Regulatory Affairs Department
CCS Associates
[name]
[name]
[name]
[contact]
[contact]

E-mail Submissions:

[contact]

Regulatory documents that do not require an original signature may be sent electronically to the Consortium Lead Organization for review, which will then be electronically forwarded to the DCP Regulatory Contractor.

14.6 Other

This trial will be conducted in compliance with the protocol, Good Clinical Practice (GCP), and the applicable regulatory requirements.

